8.4 METHOD OF ASSIGNING PATIENTS TO TREATMENT GROUP

Patient will be randomized following a 1:1:1 ratio to one of the three treatment arms via a centralized randomization system using IVRS/IWRS.

A randomized treatment kit number list will be generated centrally by Sanofi. The investigational product (SAR156597 or placebo) will be packaged in accordance with this list.

At V1 (screening) the study staff will contact the IVRS/IWRS to obtain a patient number for each patient who gives informed consent.

The result from the central reviewer on diagnosis of IPF have to be obtained to validate the inclusion of patient before randomization as per inclusion criteria (See section [Section 7.1](#))

The population will be stratified according to background therapy at the moment of randomization:

- Patient with background therapy with either pirfenidone or nintedanib
- versus patient without background therapy
- It is planned to include a maximum of 66% of patients with background therapy.

Randomization will be performed at Visit 2 (Day 1) by a centralized randomization procedure using IVRS/IWRS.

Patients who comply with all inclusion/exclusion criteria will be assigned before the IMP administration on Visit 2 (Day 1):

- A treatment number in a preplanned order following the randomization list, and
- A patient number according to the chronological order of inclusion.

A patient cannot be randomized more than once in the clinical trial.

Patients who meet exclusion criteria may be re-screened once during the open screening period of study; a different patient identification will be issued. Re-screening is not permitted if the patient fails to meet inclusion criteria. There is no requirement for a waiting period between the screen-failure date and the re-screening date. The IVRs/IWRS report will flag re-screened patients. Patients that are re-screened must sign a new consent form and all Visit 1 procedures must be repeated.

The treatment kits are sufficient for 2 weeks of treatment. As the treatment duration is 52 weeks, a patient will be allocated by the IVRS to several treatment kit numbers corresponding to the same treatment arm assigned from randomization.

The details of the centralized randomization procedure and IVRS are provided in a separate manual.

8.5 PACKAGING AND LABELING

SAR156597 and Placebo will be supplied as a treatment box. Each box will contain 2 inner boxes. Each inner box will contain 2 vials. The inner boxes will be numbered as “Box 1” and “Box 2”. Box “1” or “2” will be used for administration at the instructed time.

Packaging is in accordance with the administration schedule. The content of the labeling is in accordance with the local regulatory specifications and requirements.

8.6 STORAGE CONDITIONS AND SHELF LIFE

All investigational Product should be stored between 2°C and 8°C (36°F and 46°F). The Investigators or other authorized persons (e.g. pharmacists) are responsible for storing the IMP in a secure and safe place in accordance with local regulations, labeling specifications, policies, and procedures.

Control of IMP storage conditions, especially control of temperature (e.g. refrigerated storage) and information on in-use stability and instructions for handling the Sanofi compound should be managed according to the rules provided by the Sponsor.

At home, the treatment kits will be stored by the patients in a refrigerator in accordance with the storage conditions indicated on the label of the IMPs.

After the supply of IMP kits to patients at the study site visits, appropriate provisions will be in place for transportation of the IMP kits from the study site to the patient’s refrigerator. As an alternative to between study site visits, the IMP may be supplied from the site to the patient via a sponsor-approved courier company where allowed by local regulations and approved by the patient.

8.7 RESPONSIBILITIES

The Investigator, the hospital pharmacist, or other personnel allowed to store and dispense the IMP will be responsible for ensuring that the IMP used in the clinical trial is securely maintained as specified by the Sponsor and in accordance with applicable regulatory requirements.

All IMP will be dispensed in accordance with the Investigator's prescription and it is the Investigator's responsibility to ensure that an accurate record of IMP issued and returned is maintained.

Any quality issue noticed with the receipt or use of an IMP (deficiency in condition, appearance, pertaining documentation, labeling, expiration date, etc) should be promptly notified to the Sponsor. Some deficiencies may be recorded through a complaint procedure.

A potential defect in the quality of IMP may be subject to initiation of a recall procedure by the Sponsor. In this case, the Investigator will be responsible for promptly addressing any request made by the Sponsor, in order to recall IMP and eliminate potential hazards.

Under no circumstances will the Investigator supply IMP to a third party, allow the IMP to be used other than as directed by this clinical trial protocol, or dispose of IMP in any other manner.

8.7.1 Treatment accountability and compliance

Measures taken to ensure and document treatment compliance and IMPs accountability include:

- Proper recording of treatment kit number or packaging number as required on appropriate electronic case report form (e-CRF) page for accounting purposes.
- All medication treatment kits (whether empty or unused) are returned by the patient at each visit when a treatment dispensing is planned.
- The site unblinded personnel tracks treatment accountability/compliance comparing the treatment number recorded on the patient booklet with the treatment number of returned treatment kits (whether empty or unused) and fills in the patient treatment log.
- The unblinded monitor in charge of the reconciliation then checks the data entered on the IMPs administration page by comparing them with the IMPs that has been retrieved and the patient treatment log form.

8.7.2 Return and/or destruction of treatments

Whenever possible all partially used, used or unused investigational product will be destroyed on site according to the standard practices of the site after reconciliation verification by the monitor.

A detailed treatment log of the destroyed investigational product will be established with the Investigator (or the pharmacist) and countersigned by the Investigator and the monitoring team.

The Investigator will not destroy any investigational product unless the Sponsor provides written authorization. When destruction at site cannot be performed, all IMPs will be retrieved by the Sponsor.

A detailed treatment log of the returned IMP will be established with the Investigator (or the pharmacist) and countersigned by the Investigator and the monitoring team.

8.8 CONCOMITANT MEDICATIONS

A concomitant medication is any treatment received by the patient concomitantly to any IMP(s). An accurate record of all prescription medications (plus any herbal supplement or over the counter medications taken specifically for the IPF condition) must be kept on the appropriate record form, including the name of the medication (international nonproprietary name), start of administration, daily dosage, and duration for such use.

8.8.1 Prohibited medications

- Use of any cytotoxic/immunosuppressive (other than prednisone less than or equal to 10 mg/day or equivalent) including but not limited to azathioprine, cyclophosphamide, methotrexate, and cyclosporine within 4 weeks prior to screening and during the course of the study.
- Use of any cytokine modulators
 - Use of any biologic agent (such as etanercept, adalimumab, efalizumab, infliximab, golimumab, certolizumab) within 12 weeks or 5 half-lives of screening, and in the case of rituximab, use within 24 weeks of screening or no recovery of CD 19-positive B lymphocytes if the last dose of rituximab has been more than 24 weeks prior to screening. The use of these biologic agents is not authorized during the course of the study.
 - Alefacept within 24 months of screening and during the course of the study.
- Use of any investigational drug within 1 month of screening, or 5 pharmacodynamic/pharmacokinetic half-lives, if known (whichever is longer), and during the course of the study. Use of stem cell therapy within 12 weeks of screening, and during the course of the study.

8.8.2 Authorized concomitant medications

- Oral corticosteroids are permitted if ≤ 10 mg/day oral prednisone or equivalent and at stable dose for at least 4 weeks prior to the randomization (baseline) visit. No change is permitted unless the patient develops an AE. Dose and any change will be recorded on the patient e-CRF.
- Pirfenidone or nintedanib administered at the recommended dosage for at least 12 weeks prior to the randomization (baseline). No change is permitted unless the patient develops an AE. Dose and any change will be recorded on the patient e-CRF. Pirfenidone or nintedanib cannot be started during the course of the study.

[For Czech Republic only, per local requirement:

- *N-acetylcysteine administered at the dosage recommended by local guidelines]*

9 ASSESSMENT OF INVESTIGATIONAL MEDICINAL PRODUCT

9.1 EFFICACY

9.1.1 Primary endpoint

The primary efficacy endpoint will evaluate the efficacy of SAR156597 on lung function and will be:

- The absolute change from baseline in % predicted FVC at 52 weeks

9.1.2 Secondary endpoints

Two key secondary endpoints will evaluate other aspects of the efficacy of SAR156597 in IPF:

- Patients experiencing Disease Progression as defined by the following events: decrease in absolute % predicted FVC ≥ 10 percent or decrease in absolute percent predicted DLCO ≥ 15 percent or lung transplant or death at 52 weeks
- Deaths (all cause) at 52 weeks

9.1.3 Exploratory endpoints

- Acute exacerbations at 52 weeks (per investigator's judgment and adjudicated cases)
- Respiratory hospitalizations and rate of non-elective hospitalizations at 52 weeks
- Change from baseline in 6-MWT distance at 52 weeks
- Change from baseline in HRCT lung interstitial score at 52 weeks
- Change from baseline in the total score of the SGRQ at 52 weeks
- Change from baseline in the total score of the EQ-5D-5L at 52 weeks

9.1.4 Assessment methods and activity parameters

9.1.4.1 Pulmonary Function Tests will include:

- DLCO: carbon monoxide diffusing capacity, corrected for hemoglobin;
- FVC: forced (expiratory) vital capacity;
- FEV1: forced expiratory volume over one second (only done at screening and at baseline)

- TLC: total lung capacity (body plethysmography) (only done at screening and at baseline)
- RV: residual volume (body plethysmography) (only done at screening and at baseline)

DLCO will be measured locally at the investigational site; spirometry test will be done locally but measured by a central laboratory.

Note: Two PFTs will be performed within 4 weeks prior to dosing one at screening and one at baseline. The first PFT will determine whether the patient qualifies for the study and the second will be averaged with the first one to establish a baseline value.

9.1.4.2 Pulse oximetry

Oxygen saturation will be assessed using pulse oximetry (SpO₂).

9.1.4.3 Lung HRCT

For confirmation of diagnosis at baseline, a lung HRCT will have to be performed unless already done within 1 year prior to screening. The HRCT will be provided to the central review panel together with histology documentation if any.

A second HRCT will be performed at the end of treatment to measure the effect on lung fibrosis using a specific scoring system.

9.1.4.4 6-MWT

The distance covered by the patient over a 6 minute walk will be measured by the investigational site staff at baseline and during the treatment and reported in meters in the e-CRF. If during visits 6, 7, 8, 9 and 10, oxygen saturation is less than 88% under ambient air at rest, the patient should perform 6-MWT under 4L oxygen.

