- k* In women of child-bearing potential. After Visit 4 (W4) between study visits the patient will have a urine pregnancy test at home on a monthly basis. Patients will be given sufficient urine pregnancy kits to take home at each successive visit for monthly testing up until the end of study visit. When the testing coincides with a study visit as indicated in the flow chart, the results should be reported in the e CRF. When the testing is done at home between study visits, the results should be collected by the Investigator during the monthly phone calls and reported in the e CRF. If any interim urine pregnancy test performed by the patient is positive, the patient should immediately report to the investigator for appropriate follow-up and pregnancy reporting as appropriate.
- l* Local tolerability of SC injections will be assessed by the study nurse either at patient's place or at the site level for the inter-visit SC injection once a week. A Patient booklet to record information on injections at home will be provided to the patient at baseline and will be reviewed at each visit by Investigator.
- m* The follow-up period with no study treatment is due for patients who discontinue permanently the study treatment OR patients who complete the study.
- n* PK samples during Visits 2-9 will be collected predose (within 2 hours before each dose administration) and PK samples during Visit 10 will be collected in the morning.
- o* ADA samples will be collected at approximately the same times as the PK samples.
- p* Additional optional sampling will be performed 5 to 10 days after last dose in a subgroup of at least 30 patients per arm.
- q* Pulmonary function tests include DLCO, FVC, FEV1, TLC and RV. FEV1, TLC and RV will only be done at screening and at baseline. DLCO will be measured locally at the investigational site; spirometry test will be done locally but measured by a central laboratory.
- r* Will be measured under ambient air for all patients. For patients under oxygenotherapy, pulse oximetry will be measured under oxygenotherapy and then, after 10 minutes breathing ambient air at rest.
- s* Will be performed at screening unless already done within 1 year prior to screening.
- t* At visits 6 to 10, if oxygen saturation is less than 88% under ambient air at rest, patient should perform 6-MWT under 4L oxygen
- u* EQ-5D-5L will be measured at Visit 2 (baseline visit), Visit 8 (W36) and Visit 9 (W 52).

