7.2 EXCLUSION CRITERIA

E 01. Age \leq 40 years.

E 02. IPF disease diagnosis $>$ 5 years.

E 03. Forced vital capacity (FVC) $<$ 40% of predicted value.

E 04. Carbon monoxide diffusing lung capacity (DLCO) corrected for hemoglobin $<$ 30% of predicted value.

E 05. Severe chronic obstructive bronchitis as characterized by FEV1/FVC $<$ 0.70.

- E 06. Need for 24 hrs of oxygen therapy or oxygen saturation <88% after 10 minutes breathing ambient air at rest.
- E 07. Known diagnosis of significant respiratory disorders (e.g. asthma, tuberculosis, sarcoidosis, aspergillosis, or cystic fibrosis) other than IPF.
- E 08. Pulmonary artery hypertension requiring a specific treatment.
- E 09. Currently listed and/or anticipated to be listed for lung transplantation within the next 6 months (on an active list).
- E 10. History of vasculitis or connective tissue disorders or ANCA positive.
- E 11. Known HIV or chronic viral hepatitis.
- E 12. Exclusion related to tuberculosis (TB):
- Active tuberculosis (according to WHO guidelines (25) or a history of incompletely treated tuberculosis
 - Incompletely treated latent tuberculosis (according to WHO guidelines)
 - Positive or confirmed indeterminate (2 consecutive tests) QuantiFERON-TB Gold® test at screening (regardless of prior treatment status)
- E 13. Evidence of any clinically significant, severe or unstable, acute or chronically progressive medical (other than IPF) or surgical disorder, or any condition that may affect patient safety in the judgment of the investigator.
- E 14. Acute myocardial infarction within 6 months prior to screening.
- E 15. Clinically significant abnormal electrocardiogram (ECG) at screening that may affect the conduct of the study in the judgement of the investigator.
- E 16. Clinically significant laboratory tests at screening:
- Alanine transaminase (ALT) or aspartate transaminase (AST) >2 times upper limit of normal range (ULN)
 - Hemoglobin <11 g/100 mL for male and <10 g/100 mL for female
 - Neutrophils <1500/mm³ (except <1000/mm³ for those of African descent)
 - Platelets <100 000/mm³
 - Creatinine ≥150 µmol/L
- E 17. Current history of substance and/or alcohol abuse.

E 18. Females who are lactating or who are pregnant.

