### ***Disease characteristics at baseline***

Specific disease history includes:

- IPF diagnosis algorithm: Identifiable Causes of Interstitial Lung Disease (ILD) (yes, no), Diagnosis confirmation by Central review (yes, no), IPF diagnosis based on HRCT alone OR HRCT and Surgical Lung biopsy
- HRCT UIP (usual interstitial pneumonitis) determination during adjudication (Definite UIP, Probable UIP, Possible UIP and Definitely not UIP)
- Lung Biopsy UIP determination during adjudication (Definite UIP, Probable UIP, Possible UIP and Definitely not UIP)
- Time since diagnosis of IPF (in years and by category: <1, 1-≤3 and >3 years)
- Time since first symptoms of IPF (years)
- Any acute exacerbation within the past 12 months before enrollment (yes, no) and if yes, time from most recent date of acute exacerbation (months and by category (<6 months and ≥6 months))
- Family IPF history (yes, no, unknown)
- Oxygen therapy need (yes, no) and if yes number of hours the patient is on supplemental oxygen therapy per day
- Currently taking pirfenidone or nintedanib for at least 12 weeks prior to enrollment (yes, no) and if yes, will continue with pirfenidone or nintedanib during the study (yes, no)

The following efficacy parameters will be also summarized at baseline (see definition in [Section 2.1.3](#)):

- FVC (forced vital capacity): L and % predicted (quantitative and by tercile (≤60, >60 and ≤75, >75)),
- FEV1 (forced expiratory volume in 1 second): L and % predicted,
- FEV1/FVC ratio,
- % predicted DLCO (diffusing capacity of the lung for carbon monoxide): quantitative and by tercile (≤40, >40 and ≤55, >55),
- residual volume (RV): L,
- total lung capacity (TLC): L,
- SpO2 (peripheral oxygen saturation): % under oxygenotherapy and under ambient air,
- SGRQ total score,
- EQ-5D-5L total score,
- 6MWT (6-meter walking test) distance (m),
- Total Fibrosing ILD score.

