#### 2.1.3.2.4 *Exploratory efficacy endpoints*

The other secondary efficacy endpoints are considered exploratory and include:

- Rate of acute IPF exacerbations at 52 weeks in the mITT population
- Rate of respiratory hospitalizations and rate of non-elective hospitalizations at 52 weeks in the mITT population
- Change from baseline in 6-MWT distance at 52 weeks in the mITT population
- Change from baseline in HRCT lung interstitial score at 52 weeks in the mITT population
- Change from baseline in the total score of the SGRQ at 52 weeks in the mITT population
- Change from baseline in the total score of the EQ-5D-5L at 52 weeks in the mITT population

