#### 2.4.4.2.3.3 Change from baseline in 6-MWT distance endpoint

The absolute change from baseline in 6-MWT distance endpoint will be analyzed on the mITT population. Assessments at week 52 will be used regardless of whether the patient has previously discontinued treatment. No imputation will be performed for the week 52 missing values of 6-MWT distance. Only patients having a baseline and a post-baseline 6-MWT distance values in at least one time points analysis window will be considered in the analysis.

The absolute change from baseline in 6-MWT distance at 52 weeks will be analysed using a Mixed Model with Repeated Measures (MMRM) with the fixed categorical effects of treatment arm, stratification factor (with/without Background Therapy), time point, treatment-by-time point interaction, stratification factor-by-treatment-by-time point interaction, supplemental oxygen use (Yes/No answer to the “Does the subject need oxygen therapy” question on the “Idiopathic Pulmonary Fibrosis History” e-CRF page) recorded at baseline, as well as the continuous fixed covariate of 6-MWT distance at baseline will be used. Parameters will be estimated with the Newton-Raphson algorithm, an unstructured covariance matrix will model the within-patient errors, and the denominator degrees of freedom will be estimated using Satterthwaite’s approximation.

The SAR156597 qw arm will be tested versus Placebo at a type I error level of 10% first and if significant, will the SAR156597 q2w arm be tested versus Placebo at a two-sided type I error level of 10% using the appropriate contrast. The adjusted Least Square Means (LSMeans) estimates and standard errors (SE) will be provided for each of the 3 arms, adjusted differences of means (LSMEAN differences), corresponding standard errors (SE) and 90% CIs will be assessed for each active arm versus placebo.

Descriptive statistics for values and changes from baseline in 6-MWT distance in the mITT population will be presented by treatment arm and background therapy status for each time point. The mean (SD) 6-MWT distance values and the mean (SD) absolute change from baseline in 6MWT distance over time will be graphically represented by treatment arm and by background therapy status.

The representation of LSmeans (SE) over time will be displayed by treatment arm and background therapy status.

In addition, to assess the quality of data:

- the number (%) of patients having a completed 6 minute walking test,

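### Walk tests at Visits 6 to 10 switch to 4 L oxygen once resting saturation falls below 88%, a state excluded at entry, but the SAP analyses change in distance as like for like and adjusts only for baseline oxygen need

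*Protocol*

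**What the plan says.** **Test condition.** Protocol 9.1.4.4 sets a rule for Visits 6 to 10: if "oxygen saturation is less than 88% under ambient air at rest, the patient should perform 6-MWT under 4L oxygen". Footnote t of the flow chart (Protocol 1.2) says the same. The baseline walk is at Visit 2, which the rule does not cover.

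**Entry.** E 06 in Protocol 7.2 excludes patients with "Need for 24 hrs of oxygen therapy or oxygen saturation <88% after 10 minutes breathing ambient air at rest". Oxygen for part of the day is not excluded: SAP 2.1.1 describes at baseline "Oxygen therapy need (yes, no) and if yes number of hours the patient is on supplemental oxygen therapy per day".

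**Analysis.** The endpoint is "Change from baseline in 6-MWT distance at 52 weeks in the mITT population" (SAP 2.1.3.2.4, exploratory). SAP 2.1.3.2.7 repeats the oxygen rule as a note and attaches no analysis consequence to it. The quality items it lists for the walk-test form are completion, time walked and pauses; oxygen during the walk is not among them. SAP 2.4.4.2.3.3 fits one MMRM to the change in distance. Its oxygen term is the yes/no need for oxygen therapy from the IPF history form, "recorded at baseline, as well as the continuous fixed covariate of 6-MWT distance at baseline". Missing Week 52 distances are not imputed. The weekly arm is tested against placebo at 10%, then the two-weekly arm. Appendix B lists no supportive, subgroup or other analysis for this endpoint.

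**The concern.** A change score assumes that both measurements were made in the same way. Here the later one may be made on oxygen, and the switch is triggered by the patient's own fall in saturation. If oxygen lengthens the walk, a patient who has become sicker can show less decline than an unassisted walk would have shown, or none.

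A baseline covariate cannot correct this. It is fixed for each patient, whereas the test condition changes afterwards. By including it, the SAP already treats oxygen as relevant to distance, yet it makes no provision for oxygen started under the protocol's own rule.

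At stake is how a formally tested result, reported as least-squares mean differences in metres with 90% confidence intervals, is read. A reader of those metres would not know how many walks were done under a different condition, or in which arm.

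**Working it through.** **Plan's own figure.** The documents give no sample size, SD or relevant difference for the 6-MWT. The only sample-size figure is 92 per arm for FVC (difference 5, SD 12, two-sided 5%, 80% power). It reproduces: noncentral-t power is 79.8% at 91 per arm and 80.3% at 92. This point does not depend on it.

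**Can the condition differ between baseline and follow-up?**

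1. The rule applies at Visits 6 to 10 only.
2. E 06 bars "oxygen saturation <88% after 10 minutes breathing ambient air at rest", and eligibility is reconfirmed at Visit 2. Barring an eligibility deviation, nobody meets the trigger at the baseline walk.
3. Every walk under the rule is therefore compared with a baseline walk done outside it.
4. The SAP has no post-baseline oxygen term, flag, ranking rule or sensitivity analysis for these walks.

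**Effect on one patient.** Let g be the metres gained from oxygen. The analysed change is the unassisted change plus g, so a patient whose unassisted distance fell by g metres shows no change.

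**Effect on the arms.** Let p be the share of an arm's Week 52 walks done on oxygen under the rule.

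- Shift in an arm's mean change = p × g
- Bias in the active minus placebo difference = (p_active − p_placebo) × g

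The documents give neither p nor g. Assume p of 5% to 30% and g of 20 to 80 m. An arm's mean then shifts by between 0.05 × 20 = 1 m and 0.30 × 80 = 24 m. The bias in the difference is:

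| Placebo share | Active share | g = 20 m | g = 80 m |
|---|---|---|---|
| 20% | 20% | 0 m | 0 m |
| 10% | 5% | −1 m | −4 m |
| 20% | 10% | −2 m | −8 m |
| 30% | 15% | −3 m | −12 m |

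Swapping the shares reverses the sign: with 10% on active and 5% on placebo, 0.05 × 20 = +1 m. Narrower assumptions (a gap of 2.5 to 5 percentage points, g of 30 to 60 m) give 0.025 × 30 = 0.75 m to 0.05 × 60 = 3 m. These are shifts in simple means; covariate adjustment and missing visits would alter them somewhat in the MMRM.

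**The case against.** **Direction.** A reader might infer that the rule necessarily flatters the sickest patients and pulls the arm difference towards zero. The documents do not support that. They give no effect of 4 L oxygen on distance, and the difference is biased only if crossing rates differ, with a sign that depends on which arm has more. This objection stands, and the conclusion is conditional for that reason.

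**Baseline.** A reader might also infer that every baseline walk was done without oxygen. E 06 excludes round-the-clock need, not all use, and the protocol does not say how part-time users walk at Visit 2. Some later walks on oxygen may have an on-oxygen baseline. What holds is only that no eligible patient met this rule at baseline.

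**The alternative.** Without oxygen, some patients below 88% at rest might not walk at all. Since missing distances are not imputed, the rule may keep sick patients in the data. That is fair, and the net effect against that alternative cannot be worked out from the documents. It does not make the retained walks comparable with baseline.

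**Covariate.** Using only a baseline oxygen term is not itself a fault. Post-baseline oxygen can be affected by treatment, and adding it to the model would be improper. The gap is the missing count and sensitivity analysis.

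**Already visible.** Saturation on ambient air and under oxygen is summarised separately over time (SAP 2.1.4.4), and walk completion and pauses are tabulated. Deterioration is thus not hidden altogether, but none of these outputs links it to the distances being tested.

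**Conclusion.** The concern holds in conditional form. Following the plan compares walks under the 4 L rule with baseline walks done outside it, in a formally tested endpoint, with no step that shows or tests the consequence. If oxygen lengthens the walk, decline is understated in patients who cross 88%. If the arms also differ in how many cross, the arm difference is biased: diluted if fewer cross on active, zero if equal, reversed if more cross on active.

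The size is unknown. Every figure in metres above is an assumption, and the documents contain no 6-MWT benchmark against which to call it large or small.

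It would be wrong to carry this over to the trial's main conclusions. The 6-MWT is exploratory and tested at 10%, separately from the 5% procedure for FVC and disease progression. The primary and key secondary conclusions are unaffected. This is an inexpensive improvement, not a flaw that threatens the trial.

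**What to change.** In SAP 2.4.4.2.3.3, before the first database lock:

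- **Keep the planned MMRM** as the main 6-MWT analysis and as the estimate in metres.
- **Derive a flag** for each post-baseline walk from that visit's ambient-air saturation (below 88% means the rule was triggered). Use recorded oxygen use during the walk where it is available. Pulse oximetry is scheduled at every walk-test visit and taken on ambient air for all patients, so no new data are needed.
- **Report the number of flagged walks** by arm and visit. This alone shows whether the arms differ.
- **Add one pre-specified sensitivity analysis** of the Week 52 change, using the rank ANCOVA of SAP 2.4.4.1 with baseline distance as covariate. Rank flagged walks below unflagged walks, transplants below those, and deaths lowest. State that values missing for other reasons are not imputed, as in the current 6-MWT plan, and whether the baseline oxygen term is kept.

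**Cost.** SAP wording, one derived flag, one table and one extra analysis. The sensitivity analysis gives a rank p-value rather than metres. It also places a long walk by a patient just under 88% below a short walk by one just above, which is why it should not replace the MMRM. The flag identifies who triggered the rule, not confirmed oxygen use, because the documents do not list oxygen use among the walk-test items; the table should be labelled accordingly. The clinical oxygen rule is not changed.
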